**Table D6.2b. Youth Self-Report Measures**

CONSTRUCT	SCALE	# OF ITEMS PRE	# OF ITEMS POST	CITATION / OTHER INFORMATION
Youth Functioning				
▪ Rule-breaking behavior	Subscale of the Youth Self Report (YSR)	18	18	Achenbach & Rescorla (2007)
▪ Aggressive behavior	Subscale of the Youth Self Report (YSR)	18	18	Achenbach & Rescorla (2007)
▪ Anxious / depressed	Subscale of the Youth Self Report (YSR)	13	13	Achenbach & Rescorla (2007)
▪ History of arrest	Created for this study	3	---	n/a
▪ Alcohol and drug use	Center for Substance Abuse Prevention (CSAP)Scale	12	12	SAMHSA (2006)
Parent Behavior				
▪ Supervision of youth behavior	Loeber Parenting Scale, Supervision subscale	8	8	Loeber, Farrington, Stouthamer-Loeber, & Van Kammen (1998)
▪ Discipline consistency	Loeber Parenting Scale, Discipline Consistency subscale	5	5	Loeber, Farrington, Stouthamer-Loeber, & Van Kammen (1998)
▪ Discipline effectiveness	Loeber Parenting Scale, Discipline Effectiveness subscale	3	3	Loeber, Farrington, Stouthamer-Loeber, & Van Kammen (1998)
▪ Rewards for youth good behavior	Loeber Parenting Scale, Positive Parenting subscale	9	9	Loeber, Farrington, Stouthamer-Loeber, & Van Kammen (1998)
▪ Parental surveillance and knowledge	Parent Knowledge Scale	15	15	Steinberg, Elmen, & Mounts (1989)
App Acceptability and General Technology Use				
▪ App useability / acceptability	System Useability Scale	---	10	[name] et al. (2009)
▪ Use of and comfort with technology	Survey created for this study	---	5	n/a

**App usage data.** The App Usage Data Elements document within Appendix 14 outlines the data that will be generated by app usage itself for each participant (parent and youth). Examples of fields that will be generated are number of times each app component is opened, times of day opened, and participant responses to prompts. These data will be stored on the same server where the app operates and available for download after the dyad has completed their participation.

**Daily app satisfaction ratings.** During the evening of each day the app will prompt the participant with a pop-up notice to provide three brief Likert-scale ratings of their experience with the app that day. Daily rating questions for parents and youth appear in the App Use End of Day Ratings measure in Appendix 15. Parent ratings pertain to app helpfulness, satisfaction with the app, and sense of self-efficacy in managing youth behavior. Youth ratings pertain to feeling rewarded for good behavior, satisfaction with the app, and degree of hassle in using the app. When prompted the participant will click "OK" and be taken directly to a screen containing the three questions. When the participant has completed the questions the answers will be stored on the app server for later download at the end of the usage period. Participants can elect to not answer the questions when prompted, and prompts will not affect the participant's ability to use the phone.

**Qualitative exit interview.** Following their completion of the post-usage assessment battery, parent and youth participants will engage in a 30-45 minute open-ended interview, either in person or by phone, with a member of the research staff. (Most are expected to occur by phone). The interview provides an opportunity for participants to say in their own words their experiences using the app and suggestions for improvement. The interview consists of 2 questions for participants in the field-based beta test group or 6 questions for those in the open trial (see Appendix 16).

## **D7. Research Methods: Therapists**

**D7.1 . Procedures: All enrolled therapists.** Note that there is no therapist version of the app, and thus the therapist's own personal or workplace mobile phone use is irrelevant to the study. However, if an enrolled therapist already uses an Android-based smartphone and would like to download the parent version of the app to familiarize him/herself with it, s/he is welcome to do so at no cost, and the research team will facilitate app installation. Downloading the app to their own phone, or using a smartphone at all, is not a requirement for enrolled therapists. If a therapist elects to download the app, s/he may use it as they wish, and no data will be collected on his/her app usage.

Research staff will offer the option of downloading the app to therapists after the consenting session is complete; if a therapist wishes to do this, an account on the VillageWhere server will be set up using the therapist's email address. Research staff will email the therapist his/her password and a link for where to download the app.

As explained in the recruitment section above, all enrolled therapists will be asked to inform eligible parent-youth dyads on their caseloads about the study using the family recruitment video, and to refer parents who verbally request more information directly to the study (by obtaining a release of information from the parent to send research staff the family's contact information). A member of the research team who has clinical training (i.e., [name], [name], or [name]) will meet with the therapist (either in person or by telephone)

one or more times to provide personalized guidance in how to talk with parents and youth about the study in ways that are not coercive.

Also, as noted, we expect that some enrolled therapists will not be able to further participate in the study because no parent-youth dyad on the therapist's caseload also was enrolled, despite referrals of one or more dyads by the therapist. To acknowledge therapists' willingness to participate and his/her family referral efforts, we will allocate two additional virtual raffle tickets to any therapist who enrolls but does not participate in the study (see Lottery Ticket Allocation section below).

**D.7.2. Procedures: Enrolled therapists with linked parent-youth dyad client participants.** Due to the linked nature of this study's design, procedures outlined in this section pertain only to those enrolled therapists for whom a parent-youth dyad on his/her caseload also was enrolled. Note that there is no pre-usage assessment session for therapist participants.

***Informing therapists of linked dyad enrollment and introductory phone call.*** As soon as a parent and youth on an enrolled therapist's caseload also are enrolled, research staff will call the therapist to inform him/her of such, the approximate date of the start of the family's usage period, and to explain next steps. This phone call, expected to take 20 minutes, will introduce the following points to the therapist and encourage the therapist to read a protocol or watch videos to learn more about each:

- a. Therapists should use an upcoming clinical session to set up the app with the parent, specifically, to type in the youth's existing behavior plan into the Game Plan feature (if a behavior plan already exists in the family) or, if one does not already exist, to create a behavior plan using Game Plan;
- b. In sessions thereafter, therapists should periodically ask the parent how his/her use of VillageWhere is going, to communicate to parents that discussing the app in sessions is welcome and appropriate (see "App Inquiries" section below);
- c. At no time should discussing VillageWhere in a session take precedence over any other clinical issue deemed more important or clinically necessary (i.e., that therapists should always use their best clinical judgment as to whether and how much it is appropriate to discuss the VillageWhere app in the session).
- d. Additional support regarding how to incorporate the app into treatment sessions is available to the therapist if desired. These include a clinical protocol, training videos, and weekly office hours.

***Training on app features and therapist role.*** After the introductory phone call, research staff will email the therapist a clinical protocol document explaining best practices for using the app with parents and youth. The protocol will outline all of the app's features and provide clinical recommendations for how to support the participating family's app use in treatment during the family's testing period.

The email will also inform the therapist that a series of brief training videos showing and explaining specific app features is available to watch if desired. Some videos will focus on the details of a specific app feature, whereas others will provide general advice for using the app clinically. Each video will have a duration of five minutes or less. Participating therapists may watch all or none of these videos, and can watch them in any order they wish at any point during their participation. The clinical protocol and video segments will be redundant in the information they provide, but will offer the therapist a range of options for obtaining information with minimum burden or time investment.

**Helping the parent set up the youth's behavior plan in the app.** The clinical protocol (and a video segment) will outline to therapists how they should help the parent set up the Game Plan feature of VillageWhere in a regularly scheduled session during the first two weeks of the family's usage period. Therapists will be asked to look at the parent's version of the app on the parent's smartphone and guide the parent through how to enter the behavioral expectations the parent has for the youth (e.g., where the youth should be and what s/he is allowed to do before school, at school, after school, and on weekends) into the app. Helping the parent to set up Game Plan will be an expectation for therapists in both the Field Test (2-week test) and the Open Trial (6-week test).

**App inquiries.** The app inquiry procedure pertains only to those therapist-parent-youth triads participating in the Open Trial. During the introductory phone call with the therapist, research staff will explain what is expected of the therapist after s/he helps the parent set up the app's Game Plan feature. Specifically, the study procedure is for the therapist to make at least two additional inquiries about the app to the parent (i.e., "app inquiries") during two different regularly-scheduled treatment sessions. Two times during the family's six-week app use testing period (during weeks 3 and 4), therapists will receive an email asking them to inquire about the family's app use during a session this week, if clinically and logistically possible. Emails will be similar to the following: "This is a friendly reminder to please make your FIRST (SECOND) "app inquiry" with your linked parent during a session this week, if you have not already done so. Remember that an app inquiry involves simply asking your linked parent if s/he has any questions about the VillageWhere app or wants any help with it. As always thanks for helping with the VillageWhere project, and contact us if you need anything. Research Team."

The purpose of app inquiries is to ensure that the linked parent is explicitly invited to obtain support in using the app as part of treatment, but does not experience pressure from the therapist to use or discuss the app. Therapists will be asked, as part of their post-usage assessment battery, whether or not they discussed the app in treatment and if so, how extensive was the support provided. We expect natural variability on this dimension and will examine this variable's association to parent and youth usage data and clinical outcomes.

**Optional "Office Hours" for additional therapist support and troubleshooting.** Therapists can elect to participate in "office hour" conference calls over the course of his/her linked family's testing period for app support and to have questions answered. Office hours will be led by a clinically trained research staff member (Drs. [name], [name], or [name]) and attended by the research assistant (who will have the most information about troubleshooting the app itself). All enrolled therapists with a family in their testing period are welcome (but not required) to attend. Several such calls, each lasting one hour, will occur at various times throughout the week, and therapists may call in to whichever one best fits their schedule and remain on the call for as long as they wish. Therapists will be informed that if none fit his/her schedule they are welcome to contact [name] or the study research assistant directly at any time to have questions answered. This service is offered to therapists to increase their comfort level in being able to answer any questions a family might have or to address concerns. A log of questions raised during office hours will be kept to inform future app development.

**Post-usage assessment battery and exit interview.** On or about Day 15 (for therapists linked to a field-based beta testing family) or Day 46 (for those linked to an Open Trial family), the research assistant will email the therapist requesting that s/he complete the post-usage assessment battery on their computer using RedCap. Questionnaires inquire about therapist demographics, professional credentials, and opinions about the app. Once completed,

the assistant will schedule an “exit interview” with the therapist, lasting approximately 60 minutes, during which the participant will have an opportunity to share thoughts and opinions about the experience of using the app and offer any suggestions for improvement (see Exit Interview in Appendix 16 for interview questions). Exit interviews are expected to occur mostly by phone but will be done in person if feasible and desired. Once both the assessment battery and exit interview are completed, therapists will be mailed a check for \$50 as compensation for study participation.

**D7.3: Measures: Therapists.** Enrolled and participating herapists will provide data in two ways: 1) completing three questionnaires after all of their linked parent-youth dyads have completed study procedures; and 2) participating in an exit interview with study staff.

**Self-report questionnaires.** Table D7.3 outlines the measures that will be administered to enrolled therapists who have a linked parents-youth dyad. Full questionnaires are provided as Appendix 17 to this protocol. A therapist demographics measure asks about personal and professional characteristics and is collected for the purpose of describing the sample. Therapists will complete the brief technology use and comfort questionnaire created for all participants in this study, and will complete an additional survey regarding experiences with VillageWhere from the therapist perspective.

All therapist self-report measures will be collected one-time only, at the end of their participation in the study (i.e., when their last linked parent-youth dyad finishes its usage period and post-usage data collection sessions). Questionnaires will be entered into the RedCap system for data collection.

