Because we expect that initial markets for VW will be parents who learn of the technology in the context of treatment (i.e., their treatment providers recommend that they use the app to help meet treatment goals), mental health therapists working with the population will also be recruited as research participants. Therapists will be offered training in app features and will receive a guidebook about the app for reference. [name], one of the study PIs, a child clinical psychologist, and an expert in empirically-supported treatments for youth externalizing behavior problems, will create a 30-minute training video and deliver the training content in the video. Therapists also will be given the option of downloading the parent version of the app to their own personal smartphone to facilitate their understanding and support of the app, but this will not be required. In addition, [name] will hold weekly “office hours” for the purpose of providing therapists with as-needed support and to field questions about the app and/or study procedures. When a parent-youth dyad on the therapist’s caseload completes their 2- or 6-week trial, the therapist will complete user acceptability/satisfaction measures and participate in a qualitative exit interview about the experience.

The NIMH R43 funding mechanism motivating this protocol imposes a rigorous timeline; we (the study PIs) must complete both the formative (product development, previous IRB application) and summative (current application) evaluations in a 12-16 month window that ends approximately January 2015. Although we have attempted to anticipate and articulate all study procedures in this protocol, unanticipated issues that require rapid resolution may arise. Thus, we have inserted some points of flexibility within this protocol (e.g., number of participants recruited for field based beta testing) so that we can be responsive to study needs in real time without seeking IRB protocol amendments. We will of course seek approval(s) for amendment(s) to this protocol if we find the need to do something outside of the boundary conditions described here.

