## **D4. Study Recruitment**

Since participation of the adolescent's therapist is required in order for a parent-youth dyad to be eligible for the study, therapists will be recruited first. Once enrolled, participating therapists will then assist in the recruitment of eligible parent-youth dyads from their existing caseloads. We seek a final sample size of no less than 24 therapist-parent-youth triads (i.e., 72 individual participants) who complete all study procedures. To account for potential premature participant dropout (e.g., youth is incarcerated in week 2; parent loses mobile phone service due to unpaid bills), we plan to enroll  $N = 30$  therapist-parent-youth triads. These triads will be allocated between the field test ( $n = 4-6$  triads) and the open trial ( $n = 20$ ).

Within each triad, all 3 participants must agree for any individual in the triad to complete study procedures. Among enrolled triads, all parent-youth dyads must be unique, but their linked therapist participants do not. If a given enrolled therapist's caseload yields more than one parent-youth dyad also enrolled, that therapist will be linked to more than one parent-youth dyad in the study. Thus, while the final sample size will be no less than  $n = 24$  parents and  $n = 24$  youth, it is possible that the number of enrolled therapists will be lower (e.g.,  $n = 12$  therapists, if each therapist had two parent-youth dyads from her caseload enrolled).

Conversely, we expect that for some enrolled therapists, we will be unsuccessful in recruiting any linked parent-youth dyads from their caseloads (due to disinterest in the study or ineligibility). To account for this possibility, we will continue to recruit and enroll therapists until an  $N$  of 24 parent-youth dyads completed is achieved. One implication of this approach is that more therapists may be enrolled in the study than will actually have the opportunity to engage in study procedures (e.g., we may need to enroll  $N = 40$  therapists to achieve  $N = 24$  parent-youth dyads).

The recruitment procedures that follow are informed by experiences recruiting therapists and having therapists refer parents and youth to the study during the formative evaluation of VW (previous protocol). As described below, two separate lottery drawings (one for therapists, one for parents/youth) will be used as one part of a more comprehensive recruitment strategy.

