## **D11. Data Analysis**

Data from demographics questionnaires and the Technology Use and Comfort Survey will be used to describe the sample itself. App usage and SUS data will be used to describe the success of the app itself. On the SUS, scores below a 3.5 on a five-point Likert scale (1 = poor; 2 = fair; 3 = good; 4 = very good; 5=excellent) will indicate a need for further app refinement in subsequent research. An aggregated mean score of 3.5 or higher will support app feasibility. App usage data will be aggregated and subjected to descriptive analyses to determine most preferred features and feature use sequences. Correlational analyses will link app usage data to participant satisfaction ratings and to measures of parent/youth behavior and functioning, to determine if certain app features were more highly preferred or more linked to changes in functioning than others.

Average scores on the SUS will also be compared between parents and adolescents. Between-group comparisons on the USAS will involve independent samples t-tests; effect size estimates also will be computed.

Pre- to post-usage change will be assessed on all parent and youth measures of functioning and behavior. Paired-samples T tests will be used and effect sizes obtained.

Qualitative data obtained from exit interviews will include annotations from investigators noting likes, dislikes, points of confusion, suggestions for improvement, misunderstandings, and potential unintended consequences. Qualitative data will be analyzed using a grounded theory approach (a data-reduction method for qualitative data used to generate and test hypotheses from the ground up).

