Parent participants will likely be experiencing some distress caused by factors related to the adolescents' need for mental health treatment. Some may have mental health symptoms of their own (e.g., depression, anxiety). Therapist participants are not expected to be experiencing any distress or symptoms.

Parent and youth participants will be asked to download and use a new mobile phone application designed to help them meet one of their treatment goals, namely, better parental management of youth behavior. Participants will use the app as they wish over a 2- or 6-week testing period, and app usage data will be obtained. They will participate in pre- and post-usage assessment sessions and an exit interview post-usage. After receiving training, therapist participants will be asked to help parents set up the behavioral management feature of the app

as part of a regularly-scheduled treatment session and to offer the parent help using the app if desired. Once the app use testing period is over for their linked parent-youth dyad, therapists will answer questionnaires about the technology and participate in a qualitative exit interview.

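### A single therapist questionnaire after the last linked family conflicts with per-family timing elsewhere and can weaken the planned link between therapist support and family outcomes

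*Combined protocol and SAP*

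**What the plan says.** The timing of the therapist questionnaires is given in four places.

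- **D7.3 (Measures: Therapists):** "All therapist self-report measures will be collected one-time only, at the end of their participation in the study". The section states the rule twice and defines the end of participation by the therapist's last linked dyad.
- **D1 (Overview):** when a dyad on the caseload "completes their 2- or 6-week trial, the therapist will complete user acceptability/satisfaction measures".
- **D7.2 (Post-usage assessment battery and exit interview):** the request goes out "On or about Day 15 (for therapists linked to a field-based beta testing family) or Day 46" for those linked to an Open Trial family.
- **E1 (Human Subjects Involvement and Characteristics):** "Once the app use testing period is over for their linked parent-youth dyad, therapists will answer questionnaires".

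D4 allows for a therapist whose caseload yields more than one enrolled dyad: "that therapist will be linked to more than one parent-youth dyad in the study". Its example is 12 therapists with two dyads each.

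Under App inquiries, D7.2 says the post-usage battery will ask therapists "whether or not they discussed the app in treatment and if so, how extensive was the support provided", and that the study will examine this variable's "association to parent and youth usage data and clinical outcomes". D11 does not list that analysis. Its nearest statement concerns app usage: "Correlational analyses will link app usage data to participant satisfaction ratings and to measures of parent/youth behavior and functioning". D11 makes no allowance for dyads that share a therapist.

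**The concern.** For a therapist with one dyad the two timings nearly coincide. For a therapist with two dyads at different stages they cannot both be followed. Staff working from D7.2 would send the request at the first family's Day 46, and staff working from D7.3 would wait for the second family to finish.

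App usage and clinical outcomes are measured per family, so the support variable needs to be as well. Under D7.3 as described, a therapist with several dyads gives one retrospective report, and nothing says how it is assigned to the families. Two things could follow. Differences in support between one therapist's families are lost, which weakens the observed association. And if the same score is copied to several families that are then treated as independent, the false-positive rate can rise. D4 also does not bar a therapist from having both a field-test and an Open Trial family. The app-inquiry procedure applies only to the Open Trial, so one report could mix two procedures.

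**Working it through.** The plan gives no sample size, power, significance level or effect size for this association, so there is no figure of its own to reproduce. The one related figure is consistent: 24 dyads / 2 per therapist = 12 therapists, as in D4's example.

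**Inputs from the plan.** 20 Open Trial dyads (D6.1); more than one dyad per therapist allowed, with two each as the example (D4).

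**Assumed inputs.** True dyad-level correlation r = 0.5; within-therapist correlation of support ρ from 0 to 0.8; therapist intraclass correlation (ICC) of the outcome residual 0 or 0.3; two-sided 5% test.

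**Large-sample formulas.** With m dyads per therapist sharing one score:

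- score is the average over the therapist's families: observed r = r × √[(1 + (m−1)ρ)/m]
- score reflects the last family only: observed r = r × [1 + (m−1)ρ]/m

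For m = 1 both factors equal 1. For m = 2 and r = 0.5:

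| ρ | averaged report | last-family report |
|---|---|---|
| 0 | 0.5 × 0.707 = 0.354 | 0.5 × 0.50 = 0.250 |
| 0.3 | 0.5 × 0.806 = 0.403 | 0.5 × 0.65 = 0.325 |
| 0.5 | 0.5 × 0.866 = 0.433 | 0.5 × 0.75 = 0.375 |
| 0.7 | 0.5 × 0.922 = 0.461 | 0.5 × 0.85 = 0.425 |
| 1 | 0.500 | 0.500 |

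By the Fisher z approximation with n = 20, power at r = 0.5 is 0.62. Over ρ from 0 to 0.7 it becomes 0.33–0.54 with the averaged report and 0.18–0.47 with the last-family report. A large simulation of the m = 2 case agrees. It also shows that with an averaged report the regression slope stays at about 0.50 and only correlation and precision fall, whereas with a last-family report the slope shrinks too (0.25 at ρ = 0).

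**Simulation at the actual size.** 20 dyads, 40,000 runs per cell. Support S has within-therapist correlation ρ; outcome Y = 0.5 S + √0.75 E, where E has the stated ICC. The single score is copied to each of the therapist's families and tested with Pearson's r.

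- *20 therapists, one dyad each:* mean r 0.49, power 64%, type I error 0.05. No loss.
- *15 therapists, five with two dyads:* averaged report 0.42–0.47 (power 48–60%); last-family report 0.37–0.46 (38–58%); dyad-level reports 0.48–0.49.
- *10 therapists, two dyads each:* averaged report 0.33–0.45 (31–55%); last-family report 0.24–0.42 (17–51%); dyad-level reports 0.48–0.50 (61–65%).

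Type I error in the last case is 0.05–0.09 with copied scores and 0.05–0.08 with dyad-level scores when clustering is ignored in both. The gap depends on ρ. At ρ = 0 and ICC 0.3 it is about 0.09 against about 0.05; at ρ = 0.8 the two are close.

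**The case against.** The strongest reply is that D1, D7.2 and E1 are written in the singular and describe the ordinary one-dyad case. On that reading D7.3, the only section that addresses several dyads, is the specific rule. D9's single payment of $50 to a participating therapist fits this. It is a fair reading of intent, but it leaves D7.2's Day 15/Day 46 instruction impossible to follow for a multi-dyad therapist, and it does not make one report suit a family-level analysis.

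Second, the survey in Appendix 17 was not available. If it asks about each family separately, most of the attenuation disappears; late recall for families that finished early, and the timing conflict, would remain.

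Third, two dyads per therapist is only an illustration. D4 also counts 72 individuals for 24 triads, and up to 40 therapists may enrol for 24 dyads, so one dyad each is quite compatible with the plan. That stands: the number of multi-dyad therapists is unknown, and with five of 15 therapists having two dyads and an averaged report the loss is small beside the sampling error of a correlation on 20 dyads.

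Fourth, part of the type I inflation comes from ignoring clustering and not from the single report. This also stands in part, but where support varies freely within therapist (ρ = 0) nearly all of the excess comes from copying the score.

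Finally, the analysis is exploratory with no power claim, and even ideal data give only 61–65% power at r = 0.5. That limits the importance of the point but does not remove it.

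**Conclusion.** The concern holds. The sections conflict on when, and in effect how often, therapists report. The D7.3 rule gives a poorer measure for an analysis that D7.2 commits to.

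The size depends on unknowns: how many therapists have more than one dyad, how much their support differs between families, and whether Appendix 17 asks per family. Under the assumptions shown, an expected correlation of about 0.49 falls to between 0.24 and 0.45 if every therapist has two dyads, to between 0.37 and 0.47 if five of 15 do, and not at all if none does or if support is identical across a therapist's families. Variation between therapists is still captured. The System Usability Scale, app usage and pre-post analyses do not use this questionnaire. The change is worth making because it is cheap and because differences between families that are not recorded at the time cannot be recovered reliably later.

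**What to change.** - **D7.3:** record the therapist support items once per linked dyad, keyed to the dyad's ID, at the end of that dyad's usage period (the D7.2 timing). Keep demographics and technology comfort as one-time items.
- **D1, D7.2, D7.3 and E1:** align the wording so that all four give the same timing.
- **D11:** list the association between support and family usage and outcomes as exploratory, at dyad level within the Open Trial. Allow for shared therapists with a therapist random effect or a cluster method with small-sample correction, and report the number of dyads per therapist. If almost all therapists have one dyad, a simple correlation with its confidence interval is enough.

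The cost is a few repeated items, drawn from a six-item survey, for therapists with more than one dyad, plus minor RedCap set-up. No extra participants are needed.
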